8. RESEARCH QUESTION AND OBJECTIVES

Data from real-world setting will provide information on afatinib first-line treatment in Chinese patients diagnosed with advanced EGFR mutation-positive NSCLC.

Primary objective:

- The primary objective of this study is to assess the time on treatment of afatinib as first-line therapy in advanced non-small cell lung cancer patients with EGFR mutation. Time on treatment (TOT) is defined from the start of afatinib treatment until the end of the afatinib treatment or death date by any cause. Patients that are lost to follow up or withdraw before the end of study will be censored at the time of last known contact..

Secondary objective:

- To assess objective response rate , overall survival and safety of afatinib first-line therapy in advanced NSCLC patients with EGFR mutation.

Exploratory objective:

To collect data on acquired resistance mechanism (T790M mutation, etc) to afatinib first-line therapy.

9. RESEARCH METHODS

9.1 STUDY DESIGN

This is a NIS to be conducted at approximately 10 sites in China where real world data are from EGFR mutation positive NSCLC patients who will initiate afatinib as first-line treatment and receiving subsequent therapy. All the study sites will need to have afatinib used in regular clinical practice. Participating investigators will screen patients for eligibility, obtain informed consent, and enrol patients who meet the eligibility criteria. Investigators or trained site personnel will then complete the eCRF to capture information on demographic, medical history, and treatment information at the time of enrolment.

This study will only include patients who are newly diagnosed and who will receive afatinib as first-line treatment, regardless if they will receive 3rd generation or other treatment subsequently. Data will be collected for the patients who receiving afatinib first-line therapy and subsequent therapy. Data of patients' resistance mechanism after afatinib treatment will also be collected.

Day 0 is the date that the patient sign the informed consent . Day 1 is the first dose of afatinib. We collected the date of initial and metastatic diagnosis. Day 1 is the first dose of afatinib therapy (index date). The patients will be followed up by regular visits according to institution standards after start of afatinib until death, lost to follow-up, withdraw from the study, or end of the study for other reasons, whichever comes first and no later than Dec 2023. Please refer to [Section 4.1](#) for the visit plan and major information collected during each visit.

This study is descriptive only and there are no comparisons between groups. To assess the presence of this bias (discussed in [Section 9.9](#)), data from 1200.0066 study [where patients were diagnosed with locally advanced or metastatic NSCLC harbouring EGFR mutation(s)] may be used to verify if this study contains potential channelling bias.

9.2 SETTING

76 patients, who are diagnosed with locally advanced or metastatic NSCLC (with activating EGFR mutation) and will be treated with afatinib as fist line treatment, are be enrolled into this prospective NIS across multiple centres in China.

Eligibility will be assessed prior to enrolment during a scheduled visit. Patients who fulfil eligibility criteria as well as agree to participate in the study by signing an informed consent (required by local regulation and legal requirement) will be included into the study.

Participation of patients in this study is not intended to change the routine treatment that patients receive as determined by their clinicians; all treatment decisions, type and timing of disease monitoring are at the discretion of the treating physician. Patients will be followed by regular visits according to institution standards after the treatment is initiated. Study sites

Site selection criteria in China:

Proprietary confidential information © 2022 Boehringer Ingelheim International GmbH or one or more of its affiliated companies

- Sites prescribe afatinib on a regular clinic basis to patients with EGFR mutation-positive NSCLC
- Capability of conducting an NIS, including qualification, experience, availability and research resource of investigators
- A genetic test [(next-generation sequencing (NGS) or polymerase chain reaction, (PCR)] is applicable for patients diagnosed with NSCLC

After completing the sites feasibility for this study, 10 study sites participated in this prospective observational study.

Table 2. Study Sites

No	City	Site
1	Beijing	
2	Chengdu	
3	Zhengzhou	
4	Hangzhou	
5	Haikou	
6	Zhongshan	
7	Guangzhou	
8	Guangzhou	
9	Shenyang	
10	Shenzhen	

9.2.1 Study population

Eligible patients will be enrolled in this study and will receive afatinib (first-line) and subsequent treatment (second-line) of either 3rd generation EGFR TKI or other treatments.

Patients who are administrated with afatinib as first-line treatment started from May 2020 (first patient enrolled) and will be followed up until death, lost to follow-up, withdraw from

Proprietary confidential information © 2022 Boehringer Ingelheim International GmbH or one or more of its affiliated companies

the study, or end of the study for other reasons, whichever comes first and no later than Dec 2023.

9.2.2 Study duration

It is anticipated that all data collection for this study started from May 2020 (first patient enrolled) and will continue until Dec 2023 or the event of OS . The maximum duration of data collection for an individual patient will be a maximum of 33 months. this period may be truncated due to treatment switching, patient withdrawal from the study, or death or end of study for any other reason.

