Name of finished medicinal product: Giotrif®				
Name of active ingredient: Afatinib				

withdraw before the end of study will be censored at the time of last known contact.
 
Secondary outcomes
 
Overall survival (OS) from the start of afatinib until the date of death, loss to follow up (including patient withdrawal) or end of study period
 
Objective response rate (ORR), [objective response is defined as best overall response of complete response (CR), partial response (PR)] according to RECIST 1.1 with afatinib first-line therapy
 
Adverse events (AEs), serious adverse events (SAEs), afatinib-related AEs (ADRs) as indicated by incidence, seriousness and intensity graded according to United States (US) national cancer institute's (NCI) common terminology criteria for AEs version 5.0 (CTCAE Version 5.0)
 
Further outcome
 
Resistance mechanisms (Type and proportion:T790M,etc) after afatinib first-line treatment.
				
Data sources:	
Data for this study will be obtained via the following sources:
 
- Patient medical information: The investigator or authorized medical staff will record clinical and treatment data from patients' medical records into an electronic case report form (eCRF) at baseline and at every visit up to end of the follow up period (refer to Section 9.4)			
Study size:	76 patients			
Study duration:	The duration of data collection for an individual patient will be a maximum of approximately 33 months, It is anticipated that all data collection for this study started from May 2020(first patient enrolled) and will continue until December 2023 (two years after the last patient was enrolled)			
Data analysis:	
Time on treatment (TOT) will be analysed using Kaplan-Meier method, and the median Time on Treatment (TOT) along with two-sided 90% confidence interval (CI) will be calculated. Overall survival (OS) will be analysed similarly.
 
Objective response rate (ORR) and acquired resistance mutation type, and AEs will be summarised descriptively by frequency and proportions.
			
Milestones:				
IRB/IEC Approval: May 2020				
First Patient In: May 2020				

Name of company: Boehringer Ingelheim		
Name of finished medicinal product: Giotrif®		
Name of active ingredient: Afatinib Last Patient In: Dec 2021 Interim Analysis: Dec 2022 Last Patient Out: Dec 2023 Database Locked: Mar 2024 Final NIS Report: Jun 2024		

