4.1 FLOW CHART

Table 1. Patient Flow Chart

Procedure	Baseline	Treatment (first-line)	Treatment (second-line)	Further subsequent treatment(s) up to death	End of study (Until Dec 2023 or death)
Observation period	Before initiation of afatinib	Initiation of afatinib first-line treatment: Followed by regular visits according to institution standards	Start second-line treatment (first visit \leq 1 months followed by regular visits according to institution standards)	Start further subsequent treatment(s) followed by regular visits according to institution standards	
Informed consent ^a	X				
Demographics (age, gender, height, etc.)	X				
Body weight	X	X			
Presence of brain metastases	X	X			
Afatinib dose		X			
ECOG Performance Status	X	X			
Baseline characteristics	X ^a				
• Type of EGFR mutation at start of afatinib therapy					
• Genetic testing information ^b					
• Disease stage					
• Comorbidities					

• Medical history					
Laboratory testing information ^c	X	X			
Eligibility (I/E criteria)	X				
Administration/Concomitant therapies	X	X	X		
Tumour assessment according to local institutional standards ^d	X	X	X		
Patient vital status	X	X	X	X	X
Regular follow-up		X	X		
Genetic testing ^b			X ^f		
Adverse events (AEs)	X	X	X ^e	X ^e	X ^e

^a: Written informed consent must be obtained before any screening/baseline data collection are performed.

^b: Genetic testing report (including PCR, NGS, etc.) will be collected if available

^c: Detailed Laboratory tests are included in [section 9.3.3](#). The estimated GFR (glomerular filtration rate) using modification of diet in renal disease (MDRD) formula, eGFR = 186 x SCr (mg/dL)^{-1.154} x Age^{-0.203} x (0.742 if female) ([R02-2529](#)).

[figure not shown]
^d: Tumour assessment will only be applied while patients with anti-tumour therapy (first-line and second-line or later lines). If the treatment finish, the assessment will end.

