9.7.1 Main analysis

All patients treated with afatinib will be included in the analysis of the primary outcome, Time on Treatment (TOT) on afatinib. Time on Treatment (TOT) will be evaluated by Kaplan-Meier analysis. Median Time on Treatment (TOT) and two-side 90% CI, and the quartiles will be calculated from the Kaplan-Meier curve. Patients who are lost to follow up without providing the end date of treatment with afatinib will be censored at the time of last known contact.

Overall survival (OS) will be evaluated by Kaplan-Meier analysis. Median overall survival (OS) and two-side 90% CI, and the quartiles will be calculated from the Kaplan-Meier curve. Patients who are lost to follow up (including patient withdrawal) without providing the end date of treatment will be censored at the time of last known contact. Patients who reach the end of study period without providing the end date of treatment will be censored at the end of study.

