9.9.1 Lost to follow-up

All patients will be followed up until the event of OS. If a patient misses more than 1 clinic care visit, the site will attempt to communicate with the patient and document the patient's reason for not returning. Sites will be requested to contact patients at various times of the day and evening and on different days of the week. If the patient cannot be contacted after the due diligence process, the treating physician will attempt to contact the patient's designated secondary contacts, including the patient's general practitioner and next-of-kin or out-of-household contacts to obtain information on the patient's whereabouts and vital status. If the patient's care has been transferred to another healthcare professional, the treating physician at the enrolling site will be responsible for obtaining the required follow-up information from the new treating physician. Patients who do not return for at least 2 scheduled visits, and for whom no information is available will be considered lost to follow-up and will be censored at time of last visit or last known contact with the healthcare provider.. Follow-up information collecting could be accepted by phone call if the information is available and complete.

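### The 33-month per-patient maximum disagrees with the protocol's own dates (about 43 months), and section 9.2.2 lets data collection stop at treatment switching, against every other follow-up rule

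*Protocol*

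**What the plan says.** Protocol 9.2.2 first says that collection runs from May 2020 until December 2023 or death. It then says that the maximum for "an individual patient will be a maximum of 33 months. this period may be truncated due to treatment switching", alongside withdrawal, death and other ends of study. The abstract repeats the figure: "The duration of data collection for an individual patient will be a maximum of approximately 33 months". It does not mention switching, and it adds that collection "will continue until December 2023 (two years after the last patient was enrolled").

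The milestones (abstract and section 6) are first patient in May 2020, last patient in December 2021 and last patient out December 2023.

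The other follow-up rules are:

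- Protocol 4.1, flow chart: vital status is marked in every column, including "Further subsequent treatment(s) up to death".
- Protocol 9.1: follow-up to death, loss, withdrawal or end of study, "whichever comes first and no later than Dec 2023".
- Protocol 9.2.1: patients start afatinib "and will be followed up until death, lost to follow-up, withdraw from" the study, with the same December 2023 limit.
- Protocol 9.9.1: "All patients will be followed up until the event of OS".
- Protocol 9.7.1, on OS: "Patients who reach the end of study period without providing the end date of treatment will be censored at the end of study".
- SAP 7.7.1: survivors are censored at last known contact, and a swimlane plot of OS by subsequent treatment is planned.

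**The concern.** A maximum of 33 months cannot stand beside dates that allow the first patient about 43. Taken literally, a patient enrolled in May 2020 would leave data collection in February 2023, ten months before the study ends.

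Listing treatment switching as a reason to truncate also contradicts the follow-up rules above. It would remove the post-switch data that the SAP's swimlane plot needs.

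OS is a named secondary outcome. Follow-up that was never collected cannot be restored by the SAP's censoring rule. Switching usually follows progression, so stopping there would both lose deaths and make the censoring depend on prognosis.

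**Working it through.** **Dates.**

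- May 2020 to December 2023 is 3 × 12 + 7 = 43 months (42 to 44, depending on the days within the months).
- December 2021 to December 2023 is 24 months. Accrual lasts 43 − 24 = 19 months.
- The stated 33 does not reproduce as a maximum. The nearest match is mean potential follow-up under uniform accrual, (24 + 43)/2 = 33.5, but both places call it a maximum.

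**Patients beyond 33 months.** These are the patients enrolled in the first 43 − 33 = 10 of the 19 accrual months. The accrual pattern is an assumption.

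- Uniform: 10/19 = 53%, or 40 of 76.
- Linearly back-loaded: (10/19)² = 28%, or 21.
- Linearly front-loaded: 1 − (9/19)² = 78%, or 59.

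**Expected deaths, cap alone.** The documents give no OS planning assumption. Take exponential OS with a 30-month median (λ = ln 2/30), N = 76, potential follow-up F uniform on 24 to 43 months, and no dropout. Deaths = 76 × mean of [1 − exp(−λF)].

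- Full follow-up: the mean of exp(−λF) is (0.5743 − 0.3703)/(19λ) = 0.465, so 76 × 0.535 = 40.7.
- F limited to 33: (0.5743 − 0.4665)/(19λ) + (10/19) × 0.4665 = 0.491, so 76 × 0.509 = 38.7.

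The loss is 2 deaths. With 30% dropout (timing assumed: exponential, 30% by 33.5 months) it is about 1.4.

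**Is the OS median still estimable?** At a 30-month median, true survival is 0.467 at month 33 and 0.370 at month 43, so the cap leaves the curve only just below one half. The figures below come from 20,000 simulated studies per case, with N = 76, uniform accrual and a Kaplan-Meier log-log 90% interval. Each cell gives uncapped → capped.

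| Assumed OS median (months) | Median reached, no dropout | Median reached, 30% dropout | Upper 90% limit reached, 30% dropout |
|---|---|---|---|
| 24 | 99.7% → 97% | 99% → 96% | 79% → 54% |
| 30 | 94% → 71% | 90% → 69% | 39% → 13% |
| 33.3 | 84% → 48% | 79% → 48% | 22% → 5% |
| 36 | 73% → 31% | 69% → 32% | 14% → 2% |

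**Truncation at switching, OS median 30 months, no cap.** Protocol 9.5 assumes a 12-month median time on treatment, a hazard of ln 2/12 = 0.0578 per month. Two models were used:

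- A: the 0.0578 includes death, so the switch hazard is 0.0578 − 0.0231 = 0.0347.
- B: an independent switch hazard of 0.0578.

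If every patient can switch and h is the sum of the two hazards, deaths = 76 × (λ/h) × mean of [1 − exp(−hF)].

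- A: 76 × 0.400 × 0.848 = 25.8.
- B: 76 × 0.286 × 0.927 = 20.1 (simulated 20.3).

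For smaller switching shares, the simulated deaths (4,000 replicates) are:

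| Share who can switch | A, no dropout | B, no dropout | A, 30% dropout | B, 30% dropout |
|---|---|---|---|---|
| None (no truncation) | 40.7 | 40.7 | 34.8 | 34.8 |
| 50% | 33.3 | 30.5 | 28.8 | 26.4 |
| 70% | 30.3 | 26.3 | 26.4 | 23.1 |
| 100% | 25.8 | 20.3 | 22.8 | 18.1 |

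**Time on treatment.** With 30% of patients removed, expected events are 0.7 × 64.5 = 45.1 on full follow-up and 0.7 × 63.0 = 44.1 with the cap. Truncation at switching matters little, because afatinib has ended by then.

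**The case against.** The harm is conditional. The flow chart, 9.1, 9.2.1, 9.9.1 and the OS analysis rules all point to full follow-up, and only one sentence in a descriptive section says otherwise. OS is secondary and the study is descriptive. That stands, and it limits the severity.

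The sentence says only that the period may be truncated. It could describe the real taper after afatinib: the flow chart collects weight, laboratory tests, ECOG status and dose only to the end of first line, and collection of all adverse events ends 30 days after the last dose. This reading is possible, but 9.2.2 does not exempt vital status, and a site could as easily read it as permission to stop.

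The December 2023 date is a ceiling and partly a study-level statement, so a shorter per-patient cap might be intended. The documents cannot exclude that. A deliberate cap would still conflict with follow-up to death in 9.9.1 and with the stopping reasons in 9.1 and 9.2.1, and the OS censoring rules make no provision for it.

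The size depends on the assumed median. The only afatinib OS medians in the protocol are 31.4 and 33.3 months, both in exon 19 deletion patients, and the 36-month row exceeds both. At 20 months the cap hardly matters: with dropout, the chance of reaching the median falls from 100% to 99.7%. The switching losses require sites to stop vital-status collection despite the flow chart. These limits are fair, which is why a range is shown and no single figure.

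**Conclusion.** The concern holds. The 33-month maximum is about 10 months short of what the protocol's dates allow, and treatment switching as a truncation reason contradicts the follow-up rules elsewhere. Neither conclusion depends on modelling.

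The effect on OS is conditional on 9.2.2 being followed. The cap would cost few deaths and add no bias before month 33, but it could leave the median or its upper limit unreached if the true median is about 30 months or more. Stopping at switching is the larger risk: roughly a fifth to a half of the deaths at a 30-month median, with censoring that is probably informative. These sizes rest on uniform accrual, exponential OS, and assumed switching shares and dropout timing. The primary outcome is little affected. This should be corrected, but it does not invalidate the planned analysis.

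**What to change.** In Protocol 9.2.2 and the abstract, replace 33 months with up to about 43 months (May 2020 to December 2023). In 9.2.2 only, delete treatment switching from the truncation reasons. State there that switching ends the time-on-treatment period only, and that vital status is collected until death, withdrawal, loss to follow-up or December 2023.

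This concerns data collection, not treatment. It adds no visits or procedures, because follow-up to December 2023 and vital status through later lines are already planned. The cost is wording in two places, plus the ethics committee and authority review that Protocol 10.1 requires for amendments.

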9.2.3 Eligibility

Patients must meet all of the following inclusion criteria and not meet any of the exclusion criteria to be eligible for the study:

- Inclusion criteria:**

- Patients who are diagnosed with locally advanced or metastatic NSCLC with EGFR sensitive mutation positive
- Patients who will initiate afatinib as first-line treatment for EGFR mutation-positive NSCLC
- Male and female patients with age ≥ 18 years
- Written informed consent per local regulatory requirement

- Exclusion criteria:**

- Patients who have received previous systemic therapy (previous adjuvant or neo-adjuvant therapies are permitted)
- Patients with symptomatic brain metastases (patients with brain metastases, who were previously treated, are eligible provided they have asymptomatic brain metastasis for at least 4 weeks on stable doses of medication) at the start of afatinib treatment
- Patients with concurrent participation in an interventional oncology clinical trial during the first-line treatment phase or within the last 30 days prior to the first-line treatment phase. If patients join another interventional study during the period of second-line treatment or later-line treatment, this patient should not be excluded from this study

All patients who fulfil eligibility criteria and provide written informed consent will be enrolled

Patients' record in the study will be maintained in the ISF at the investigational sites.

[figure not shown]
9.2.4 Study visits

This NIS does not impose a therapy protocol, diagnostic/therapeutic procedure, but a regular clinical visit schedule. Patients will be enrolled in the study during a regularly scheduled clinic visit prior to initiating their treatment (Day 0). Day 1 is defined as the day that the patient initiates afatinib (index date). Patients will be followed by regular visits according to institution standards since enrolment. After progression on first-line treatment with afatinib, based on the clinical practice, patients may have an appropriate genetic examination (such as NGS or PCR) in order to identify the best treatment option based on the testing result.

Lab testing and additional procedures would be based on physician's judgement and clinical practice.

Below Figure 1 list the study flow chart and visits

Figure 1: Study Flow Chart

9.2.5 Study discontinuation

BI reserves the right to discontinue the study or at a particular study site at any time for the following reasons:

- Failure to meet expected enrolment goals overall or at a particular study site
- Emergence of any efficacy/safety information that could significantly affect the continuation of the study, or any other administrative reasons

- Violation of regulations, the study protocol, or the contract by a study site, disturbing the appropriate conduct of the study

The investigator/the study site will be reimbursed for reasonable expenses incurred in the event of study termination (except in the event of the third reason).

9.3 VARIABLES

This is a prospective, observational study. Clinical data will be collected and entered directly into the eCRF during or after the patient visit per study protocol. The study protocol does not mandate treatments, each participating site provides and documents patient care and outcomes according to usual care, physician discretion and local practice standards. Thus, study variables may not be available for all patients at all data collection time points per routine medical care. All the data will be continuously and directly into the eCRF during or after the patient visit in the whole study period.

The study variables to be collected include:

- Date of diagnosis
- Demographics: age at the start of afatinib treatment, gender, smoking status
- Laboratory test: hematology, biochemistry and urine examinations. List below table 2:

Table 3. Laboratory test

Category	Parameters
Hematology	Hemoglobin, platelet count, white blood cell (WBC), absolute neutrophil count (ANC)
Chemistry	Electrolytes: Sodium and potassium Liver function tests: Alkaline phosphatase, aspartate amino transferase (AST/SGOT), alanine amino transferase (ALT/SGPT), γ -glutamyltransferase (GGT), total bilirubin Renal function parameters: Blood urea/Blood Urea Nitrogen (BUN), creatinine Other: Glucose, albumin, phosphorus, lactate dehydrogenase (LDH), total protein,
Urinalysis	pH, protein, glucose, blood/erythrocytes, leucocytes, nitrite; in case of clinically significant finding further evaluation should be performed and results documented. Dipstick testing is sufficient.

- Stage of disease at the start of afatinib treatment
- Tumour histology

- Type of EGFR mutations at the start of afatinib and subsequent treatment, specifically the type of acquired resistance mutation
- Sites of metastases at start of afatinib treatment
- Body weight and height at the start of afatinib treatment
- Eastern cooperative oncology group (ECOG) performance score (PS) (if available) at start of afatinib treatment
- Date of start and end of afatinib treatment
- Starting dose of afatinib
- Afatinib dose modification(s) and date(s) (if applicable)
- ECOG PS (if available) at start of subsequent treatment
- Sites of metastases at the start of subsequent treatment
- Reason for discontinuation of afatinib treatment (e.g., progressive disease (PD), AE)
- If subsequent treatment was provided within an expanded access programme (EAP)/compassionate use programmes (CUP) or prescribed as clinical practice
- Comorbidities (hepatitis B, gastritis, liver cirrhosis, etc.)
- Concomitant medications including (PPIetc.)
- AEs (leading to dose modification)
- Date & Cause of death

